7 STUDY POPULATION

The study population is individuals infected with SARS-CoV-2 who have symptoms associated with COVID-19 that is either not under active medical treatment or is being treated as an outpatient. Study subjects must be symptomatic for 3 days or less and have a positive COVID-19 antigen test using an FDA authorized SARS-CoV-2 antigen diagnostic test at or within the past 24 hours of screening. Study subjects will be randomized to treatment arm within dose in a 2:1 ratio according to a fixed schedule using a permuted block design. The targeted number of subjects randomized per dose is 30 (20 volunteers to the RD-X19 arm, 10 subjects to the sham arm). This is a sample size of convenience as this is a hypothesis generating study.

The target population should reflect the subject population with uncomplicated COVID-19 in the community at large.

Subject Inclusion and Exclusion Criteria must be confirmed by a study clinician, licensed to make medical diagnoses.

7.1 Inclusion Criteria

A subject must meet all the following criteria to be eligible to participate in this study:

1. Positive for SARS-CoV-2 antigen via nasal swab at or within the past 24 hours of the screening visit detected using an FDA authorized SARS-CoV-2 antigen test.
2. Onset of signs and symptoms consistent with COVID-19* no longer than within the past 3 days* and have either a) a fever of at least 100 °F or b) at least two moderate or severe

symptoms (cough, sore throat, nasal congestion, headache, chills/sweats, muscle or joint pain, fatigue, and nausea) at the time of screening.

3. Provides written informed consent prior to initiation of any study procedures.
4. Be able to understand and agrees to comply with planned study procedures and be available for all study visits.
5. Agrees to the collection of nasopharyngeal swabs, oropharyngeal swabs, oral saliva specimen collection and venous blood specimens per protocol.
6. Agrees to refrain from using oral antiseptics (e.g. hydrogen peroxide rinse, Listerine) or mouthwashes of any kind during the study.
7. Male or non-pregnant female, 18 to 65 years of age, inclusive, at time of enrollment.
8. No uncontrolled disease process (chronic or acute), other than COVID-19 signs and symptoms*.
9. No physical or mental conditions or attributes at the time of screening, which in the opinion of the PI, will prevent full adherence to, and completion of, the protocol.

*The following COVID-19 onset of signs and symptoms generally appear 2-7 days after exposure to SARS-CoV-2:

- Cough
- Sore Throat
- Nasal Congestion
- Headache
- Chills/sweats
- Muscle or joint pain
- Fatigue
- Nausea

Severity of COVID-19 symptoms will be assessed based on definitions used for graded adverse events:

- None (Grade 0): Not present
- Mild (Grade 1): Events that are usually transient and may require only minimal or no treatment or therapeutic intervention and generally do not interfere with the subject's usual activities of daily living.
- Moderate (Grade 2): Events that are usually alleviated with additional specific therapeutic intervention. The event interferes with usual activities of daily living causing discomfort but poses no significant or permanent risk of harm to the research subject.
- Severe (Grade 3): Events interrupt usual activities of daily living, or significantly affects clinical status, or may require intensive therapeutic intervention. Severe events are usually incapacitating.

7.2 Exclusion Criteria

A subject who meets any of the following criteria will be excluded from participation in this study:

1. Positive urine pregnancy test at screening.
2. Any medical disease or condition that, in the opinion of the site Principal Investigator (PI) or appropriate sub-investigator, precludes study participation.
3. Presence of self-reported or medically documented uncontrolled significant medical or psychiatric condition(s) other than COVID-19.
4. Reports a recent positive test result (within the past 6 months) for hepatitis B surface antigen, hepatitis C virus antibody, or HIV-1 antibodies at screening.
5. Has a history of alcohol abuse or other recreational drug (excluding cannabis) use within 1 month of Study Day 1.
6. COVID-19 signs associated with acute respiratory distress or imminent serious medical outcomes. ^^
7. BMI ≥ 36
8. **Subjects living (e.g., siblings, spouses, relatives, roommates) in the same household cannot be enrolled.**
9. Has participated in another investigational study involving any intervention for SARS-CoV-2/COVID-19 within the past 6 months or any clinical trial with interventional investigational product within 30 days of screening.
10. Currently enrolled in or plans to participate in another clinical trial with an interventional investigational agent that will be received during the study period.
11. History of hospitalization within the past 60 days.
12. History of systemic antiviral therapies within the past 30 days.
13. History of oral corticoid steroid use within the past 14 days or steroid injection within the past 6 months. Active use of nasal or inhalable steroids is also exclusionary. Topical steroids are not exclusionary.
14. Has a history of hypersensitivity or severe allergic reaction (e.g., anaphylaxis, generalized urticaria, angioedema, other significant reaction) to nitrates, nitrates or sun exposure.
15. Has any oral abnormality (e.g. ulcer, oral mucositis, gingivitis) that in the opinion of the investigator would interfere with device use, or intra-oral metal body piercings that cannot be removed for the duration of the study. Metal orthodontia is permitted as braces will be covered by the device mouthpiece.

^^Potential Study Subjects Presenting with any of the following should be referred for immediate medical care and are not eligible for the study:

- Fever $> 104^{\circ}$ F
- Cough with sputum production
- Rales and/or rhonchi
- Difficulty breathing or respiratory distress defined by a respiratory rate ≥ 30 per minute, heart rate ≥ 125 per minute, $\text{SpO}_2 \leq 93\%$ on room air at sea level or $\text{PaO}_2/\text{FiO}_2 < 300$.
- Persistent pain or pressure in the chest
- Confusion

7.3 Study Volunteer Selection, Retention & Compensation

7.3.1 Recruitment

Potential subjects will learn about the study via IRB-approved recruitment strategies, including direct mailing, recruitment from an IRB-approved trial registry, digital advertisements and local advertisements/flyers. Pre-screening may begin with a brief IRB-approved telephone call from study staff. Information about the study will be presented to potential subjects and questions about their health and ability to comply with the study visit schedule will be asked of potential subjects to presumptively determine eligibility. Appointments will be made at the clinical trial unit for potential subjects who are interested in the study for further screening procedures and additional protocol-specific information.

7.3.2 Retention

Study retention strategies will include education and explanation of the study schedule and procedures during screening and enrollment visits and restriction of enrollment to persons who can attend all study visits. Participating subjects will be reminded of subsequent visits during each visit, and study staff will contact subjects prior to appointments. Study staff will contact subjects who miss appointments to encourage them to return for completion of safety evaluations.

7.3.3 Compensation Plan for Subjects

Subjects will be compensated for their participation in this trial. Compensation will take into consideration both the urgency and importance of developing new treatments for this COVID-19 pandemic and local IRB guidelines, and will be ultimately subject to local IRB approval. Reimbursements will be disbursed at specific timepoints during the study with the total amount contingent on completing study procedures.

7.3.4 Costs

There is no cost to subjects for the research tests, procedures/evaluations or study device while taking part in this trial. Procedures and treatment for clinical care may be billed to the subject, subject's insurance or third party.

8 STUDY DEVICE

8.1 Regulatory Considerations

8.1.1 Preliminary Regulatory Pathway for EmitBio™ RD-X19

The Food and Drug Administration (FDA) plays a critical role in protecting the United States from threats such as emerging infectious diseases, including the COVID-19 pandemic. To date, the agency has utilized various mechanisms to expand access for drugs, grant emergency use authorization (EUA) for certain diagnostic and treatment approaches and has issued policies for medical devices without premarket notification during the COVID-19 public health emergency.

Risk management activities have been completed according to EmitBio's SOP for Risk Management and a Risk Management Plan was developed, which are compliant with the applicable 21 CFR part 820 regulations, ANSI AAMI ISO 14971, and ISO TR 24971. A Hazard Analysis, including a Failure Effects Mode Analysis, of the device characteristics and use was performed based on ANSI AAMI ISO 14971.

The risks identified, mitigation measures and control strategies, in combination with a review of all available nonclinical and clinical safety information, has led the company to conclude that the RD-X19 operating at the proposed fluence levels is a Nonsignificant Risk Device.

Per the FDA guidance document titled “Significant Risk and Nonsignificant Risk Medical Device Studies,” NSR device studies do not have to have an Investigational Device Exemption (IDE) application approved by FDA prior to initiation.

EmitBio™ conducted RD19-01-3Q20 under 21 CFR 812 as a Non-Significant Risk (NSR), Minimal Risk protocol. The Institutional Review Board agreed with EmitBio™ based on the protocol and supporting documentation submitted with the protocol and granted final approval to conduct the study on September 1, 2020.

8.1.2 Proposed Label Claim/Indication for Use:

The RD-X19 device is intended for use as a treatment to reduce viral load in the upper respiratory tract in subjects ages 12 to 65 who have tested positive for SARS-CoV-2 and who have symptoms consistent with uncomplicated COVID-19 for no more than 3 days.

8.1.3 Medical Device Quality System:

EmitBio™ will operate under an established Quality Management System, with a commitment for continuous improvement and effectiveness, in accordance with the requirements of the customers and applicable international standards. Specifically, the EmitBio™ Quality Management System is compliant with the requirements of the FDA Quality Systems Regulations (QSR).

8.2 Study Device and Use

8.2.1 Device Description

8.3 Use / Storage & Maintenance / Accountability

8.3.1 Acquisition and Accountability

The sponsor will provide clinical sites with RD-X19 devices packaged in appropriately labelled containers containing all components as well as instructions for use by study participants. Each RD-X19 device will be stamped on its power unit with a serial number. Study staff will ensure that each device's serial number is assigned to a specific study subject and the link between device serial number and study subject study number will be maintained on an accountability log. Subjects will be requested to bring their device to the clinic for each scheduled visit. Upon termination of a subject's participation in the trial, all RD-X19 devices and components must be returned to the study site and then to the study sponsor.

8.3.2 Device Storage and Maintenance

All RD-X19 devices will be stored in a locked device storage room at the clinical trial site until needed for assignment to an enrolled study volunteer. Upon acquisition by the study subject, devices should be stored in a dry climate-controlled environment in the original container in which it was provided.

The device should be stored securely out of the reach of children who may mistakenly misuse the device, especially illumination of eyes – which is always to be avoided. The mouthpiece of the device is removable for rinsing with mild soap and warm water. The device tongue depressor and power housing may be cleaned with a soft cloth that has been dampened in mild dish detergent diluted in water; pieces should then be dried with a soft cloth. The optic device can be wiped gently with a dry cloth suitable for cleaning optical glasses.

8.3.3 Preparation for Use and Use

[Refer to Appendix 1: RD-X19 User Instructions]

8.4 Measures to Maximize Study Subject Compliance

Randomization between active treatment and sham control devices has been set at 2:1 to provide higher probability of the subjects being randomized to the investigational treatment during the study duration.

Subjects will receive appropriate compensation for the disruption to normal daily activities created by this protocol that also considers the frequency with which they are requesting to travel to the site, the twice daily journaling and treatment regimen, and the number of biospecimens scheduled to be collected for virology assessments.

Additionally, the subjects will be educated on the role of their individual contribution in clinical research as it relates to developing a solution for the COVID-19 pandemic on a global scale.

8.5 Device Discontinuation

8.5.1 Study Pausing Criteria

EB-P12-01 enrollment will be paused if any of the following events occur:

- Any subject experiences an SAE after use of the RD-X19 Device that is considered related to RD-X19.
- Any subject experiences laryngospasm, bronchospasm or anaphylaxis within 2 hours after use of the RD-X19 Device that is considered related to RD-X19.
- Two (2) or more subjects experience an allergic reaction such as generalized urticaria (defined as occurring at three or more body parts) within 72 hours after administration of light that is considered related to RD-X19.
- Three (3) or more subjects experience a Grade 3 AE (systemic and/or clinical laboratory abnormality), in the same SOC grouping of Preferred Terms based on the Medical Dictionary for Regulatory Activities (MedDRA) coding, considered to be related to RD-X19.

Enrollment may resume only after external safety review of the SAE/AEs that caused the pause to the study. Given the frequency of visits and the duration of the protocol, study device use may continue after assessing the safety and AEs for individual subjects at either regulatory scheduled or an unscheduled site visits.

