4.2 Study Schedule of Activities

Study Procedures	Follow-up Period (Visit Window)				
	1	2	3	5 (-1 to +1)	8/ET (-1 to +1)
Study Days					
Informed Consent	X				
COVID19 Screening & SARS-CoV-2 Rapid Antigen Test***	X				
Medical History & Physical Examination	X	Changes since last visit only	Changes since last visit only	Changes since last visit only	X
Oropharyngeal Assessment	X*	Changes since last visit only	Changes since last visit only	Changes since last visit only	X
Urine Pregnancy Test	X				X
Concomitant Medication History/New	Baseline	Changes since last visit only			
Comprehensive Metabolic Panel & CBC	X				X
Vital Signs	X				X
Methemoglobin	X				X
Adverse Event Assessment / Reactogenicity	Baseline	X	X	X	X
Demographics, Inclusion / Exclusion Review	X				
Diary Dispensation/Collection	X				X
Treatment at Site	X**	X**	X**		
Biospecimen collection for viral assays (3 specimens)****	X		X	X	X
COVID-19 Severity Score	X				X
Collect RD-X19 Device	NA			Cohort 1	Cohort 2

*On Day 1 to be evaluated 30 minutes after first illumination at site.

**Only one treatment will be done on site, other treatment will be done at home, i.e. if afternoon appointment, subject will complete morning treatment at home and afternoon treatment administered at the site. For scheduling purposes, recommended interval between treatment is approximately 8 – 12 hours but not \leq 4 hours.

***Subjects presenting at the time of screening that have tested positive via a SARS-CoV-2 rapid antigen test at or within the past 24 hours of the screening visit and can provide documentation confirming proper identification, the date of the test and testing location, positivity of the result, and name/identity of the assay used to generate the result, are also eligible for enrollment and the rapid antigen test does not have to be repeated at the site.

**** At Baseline and days 3, 5, and 8, subjects will provide two saliva specimens and an oropharyngeal swab for virology endpoint assessments. One saliva specimen will be collected, preserved, and shipped fresh to a central lab for assessment of SARS-CoV-2 mRNA via RT-qPCR. The second specimen and the oropharyngeal swab will be collected in separate collection tubes, frozen, and stored at the site and shipped to a central lab at the end of each cohort.

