9.2.1 Definition of Adverse Event (AE)

AE means any untoward medical occurrence associated with the use of an intervention in humans, whether or not considered intervention-related (21 CFR 312.32 (a)). An AE can therefore be any unfavorable and unintended sign (including an abnormal clinical laboratory finding), symptom or disease temporally associated with the use of medicinal (investigational) product.

Any medical condition that is present at the time that the subject is screened will be considered as baseline and not reported as an AE. However, if the severity of any pre-existing medical condition increases, it should be recorded as an AE.

AEs can be further divided into solicited AEs and unsolicited AEs. Solicited AEs are those for which the study team will specifically query the subject whether they occurred. Unsolicited AEs are those events that the subject report occurring without being queried about the specific event.

All AEs will be assessed for severity and relationship to study intervention. Reporting of all AEs, solicited and unsolicited, will occur during the period from study device administration on Day 1 through Day 8 or until an early termination visit.

All AEs, solicited and unsolicited, will be captured on the appropriate source documents and e-CRFs. Information to be collected for AEs includes event description, date of onset, assessment of severity, relationship to study product and alternate etiology (assessed only by those with the training and authority to make a diagnosis as the participating clinical site PI or appropriate sub-investigator), date of resolution, seriousness, and outcome. All AEs will be documented regardless of relationship.

AEs will be followed to resolution or stabilization.

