3.1 Study Design

For the purpose of exploring the above objectives, the study will be conducted as a randomized, double-blind, sham-controlled dose escalation study in SARS-CoV-2 infected individuals with outpatient COVID-19 at two dosing schedules.

This study plans to enroll into two treatment arms within two escalating dose cohorts:

Volunteers meeting all inclusion criteria and none of the exclusion criteria will be randomized to the RD-X19 treatment arm or the sham treatment arm within each cohort in a 2:1 ratio (20 RD-X19 : 10 sham), according to a fixed schedule via a permuted block design and stratified by clinical site. Light will be administered twice daily locally to the mouth and throat only for four days for Cohort 1 and for seven days for Cohort 2.

The clinic visits will occur at:

- Visit 1 / Screening, Enrollment & Randomization

- Visit 2 / Day 2
- Visit 3 / Day 3
- Visit 4 / Day 5 (\pm 1 day)
- Visit 5 / Day 8 (\pm 1 day) / Early Termination (ET)

Assessments of treatment response will occur on study days 3 and 5, with a final determination of efficacy made on day 8 (inclusive).

Efficacy will be evaluated through evaluation of viral load through quantitation of SARS-CoV-2 mRNA by RT-qPCR and via quantitation of replication competent virus by viral titer. Severity of the symptoms of disease will also be aggregated to produce a composite COVID-19 severity score. Safety and tolerability assessments will include solicited and unsolicited adverse events (AEs), physical examinations, vital signs, and clinical laboratory tests.

One unblinded interim analysis is planned upon completion of all subjects in Cohort 1. The results of the interim analysis will be reviewed by a safety monitoring team and a recommendation will be made to the sponsor on whether enrollment should proceed for the next cohort at the next planned dose or at a reduced dosing frequency (e.g. once daily). The study is designed to evaluate at least 2 dosing schedules, ascending, or descending based on safety of each previous cohort.

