5.1 Methodological Considerations

General Conventions

SAS software (version 9.4 or higher) will be used for all data analyses and tabulations.

The study is not powered for hypothesis testing. P-values will be considered descriptive and will not be adjusted for multiplicity.

Data for all investigational centers will be pooled for analysis.

Unless specified elsewhere, baseline is defined as the last available measurement prior to administration of study drug. Change from baseline will be calculated as the post-baseline value minus the baseline value.

Summary tables will include the data based upon the protocol scheduled time points. For subjects who are early discontinued from the study, all efficacy assessments captured at the ET visit will be assigned to the nearest protocol scheduled time point.

Visit of Treatment Period	Range*	Target Day
Visit 1 / Baseline (Day 1)	Study Day = 1	Day 1
Visit 2 / Day 2	Study Day = 2	Day 2
Visit 3 / Day 3	Study Day = 3	Day 3
Visit 4 / Day 5 (± 1 day)	Study Day 4 to 6	Day 5
Visit 5 / Day 8 (± 1 day)	Study Day 7 to 9	Day 8

*Study day = date of visit - date of first treatment + 1

Descriptive statistics of continuous variables will include n, mean, standard deviation (SD), median, minimum and maximum. Generally, the minimum and maximum values will be presented to the same decimal precision as the raw values, the mean and median values to one more, and the SD, to two more decimal places than the raw values. Summaries for categorical data will include frequencies and percentages. Percentages will be presented to one decimal place.

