5.6.4 Other Assessments

Following assessment results will be presented in subject data listing: medical history, physical examination, clinical laboratory evaluations, concomitant medications.

Interim Analysis

Upon completion of all subjects in Cohort 1, an unblinded interim analysis will be conducted focusing on the following evaluations:

- Efficacy:
 - Geometric mean viral load as measured in saliva on day 1, 3, 5 and 8 by RT-qPCR
 - Proportion of subjects demonstrating viral load reduction $\geq 95\%$ on day 3, 5 and 8 by RT-qPCR.
 - Time to alleviation of COVID-19 signs and symptoms
 - Time to sustained alleviation of COVID-19 signs and symptoms
- Safety:
 - All safety tabulations as listed in section 5.6.1 will be assessed as part of the interim analysis.
 - Summary of Treatment Emergent Adverse Events including a review of listings to monitor:
 - Number of study subjects experiencing any Serious Adverse Reaction (SAE).
 - Number of study subject experiencing treatment site reactions, including pain, induration or erythema of the oropharynx or oral mucosa, including the uvula and tongue.
 - Number of study subjects with any laboratory result that is out-of-range using the testing laboratory's institutional standards, including blood, urine and methemoglobin measured by pulse oxymetry.
 - Number of subjects experiencing laryngospasm, bronchospasm or anaphylaxis within 2 hours after use of the RD-X19 Device that is considered related to RD-X19.
 - Number of subjects experiencing an allergic reaction such as generalized urticaria (defined as occurring at three or more body parts) within 72 hours after use of study treatment that is considered related to RD-X19.
 - Number of subjects experiencing Grade 3 TEAE, in the same SOC grouping of PT, considered to be related to RD-X19.

As study subjects in cohort 1 are essentially a separate study, there is no prohibition to sponsor being unblinded for the interim analysis. Cohort 1 subjects are not tied to cohort 2 in any way and unblinding data from cohort 1 has no operational or statistical implications for cohort 2 assessment by sponsor. Study site personnel may not be unblinded to cohort 1 as there is a reasonable possibility that this information could be the basis for bias in the assessment of cohort 2.

To meet above review interest, the following summary tables (treatment groups: 4 Days RD-X19 vs. Sham) and by-subject data listings will be prepared for the interim analysis:

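### The 72-hour allergic-reaction window outlasts AE collection for the last treatments of the 7-day cohort, so Cohort 2 reactions can be under-counted

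*Combined protocol and SAP*

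**What the plan says.** Protocol 8.5.1 opens with "EB-P12-01 enrollment will be paused if any of the following events occur". One listed event is two or more subjects with an allergic reaction "within 72 hours after administration of light that is considered related to RD-X19". The SAP's Interim Analysis text, after 5.6.4, counts the same event "within 72 hours after use of study treatment that is considered related to RD-X19".

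Protocol 9.2.1 sets one AE reporting period for both cohorts: "from study device administration on Day 1 through Day 8 or until an early termination visit". SAP 5.6.1 tabulates illumination-site reactions and unsolicited AEs by study day, 1 through 8.

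SAP 3.1 gives twice-daily light "for four days for Cohort 1 and for seven days for Cohort 2". SAP 5.1 maps the final visit to "Study Day 7 to 9".

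After the final visit the plan provides for three things only. AEs already recorded are followed to resolution or stabilization (9.2.1). Unresolved reactogenicity is followed (9.2.2). SAEs suspected to be related are reported if the investigator becomes aware of them (9.2.6). Section 9.2.11 covers AE recording for the duration of the study and adds nothing beyond it.

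**The concern.** The event definition looks forward 72 hours from a treatment, while data collection stops on a fixed study day. The two fit when treatment ends on Day 4. They do not fit when it ends on Day 7.

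The event most exposed is the one the criterion names: a non-serious, delayed skin reaction. If it first appears on Day 9 or 10 in a Cohort 2 subject already seen for the last time, it meets 8.5.1 but nobody is scheduled to ask about it. The trigger is two subjects, so one missed case can decide whether it is met. Safety at two dosing schedules is also part of the primary goal (4.1.1), and the SAP safety tables show the 4-day, 7-day and sham groups side by side. An under-count confined largely to the 7-day schedule therefore affects how that schedule is described.

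**Working it through.** The plan states no figure on this point, so there is nothing to reproduce. The check is timeline arithmetic.

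**Inputs from the documents.** Window 72 h (8.5.1). AE reporting to Day 8/ET (9.2.1). Final visit Day 7 to 9 (SAP 5.1). Eight treatments over 4 days in Cohort 1 and 14 over 7 days in Cohort 2 (SAP 3.1). On spacing within a day, "recommended interval between treatment is approximately 8 – 12 hours" (4.2). Twenty RD-X19 subjects per cohort (10.2).

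**Assumptions.** Clock times and reaction risks are not in the documents. Set A: treatments at 08:00 and 18:00, final visit at 10:00. Set B: treatments at 09:00 and 19:00, final visit at 12:00, first treatment in the morning or the evening of Day 1.

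**Step 1, any clock times.** A Day 7 treatment plus 72 h falls on Day 10. The latest allowed visit is Day 9. No on-schedule visit covers the window after a Day 7 treatment.

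**Step 2, treatments with an incomplete window (Set A).** A treatment is complete if given at least 72 h before the visit.

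| Final visit | Cut-off for a complete window | Cohort 2 incomplete | Cohort 1 incomplete |
|---|---|---|---|
| Day 7 | Day 4, 10:00 | 6 of the 13 given by then | 1 of 8 |
| Day 8 | Day 5, 10:00 | 14 - 9 = 5 of 14 | 0 of 8 |
| Day 9 | Day 6, 10:00 | 14 - 11 = 3 of 14 | 0 of 8 |

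At a Day 8 visit the last Cohort 2 treatment (Day 7, 18:00) is observed for 6 + 10 = 16 of 72 h.

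**Step 3, continuous at-risk time (Set B).** Step 2 counts treatments, not missed reactions: with twice-daily use the windows overlap. A better measure is

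observed fraction = (visit time - first treatment) / (last treatment + 72 h - first treatment).

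Cohort 2, Day 8 visit:
- Morning start: 171/226 = 0.757.
- Evening start, with the 14th treatment on the morning of Day 8: 161/230 = 0.700.

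At a Day 9 visit the fractions are 195/226 = 0.863 and 185/230 = 0.804. Cohort 1 at a Day 8 visit is complete: 154/154 and 158/158.

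**Step 4, Cohort 2 against Cohort 1 (Set B, Day 8 visit).**

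| Measure | Full ratio | Observed ratio |
|---|---|---|
| Continuous hours, morning start | 226/154 = 1.47 | 171/154 = 1.11 |
| Continuous hours, evening start | 230/158 = 1.46 | 161/158 = 1.02 |
| Hours summed over treatments, morning start | 1008/576 = 1.75 | 849/576 = 1.47 |
| Hours summed over treatments, evening start | 1008/576 = 1.75 | 780/576 = 1.35 |

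The excess shrinks but does not reverse. At a Day 7 visit continuous observed time is equal in the two cohorts (147 h each, or 137 h each).

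**Step 5, the two-subject trigger.** For 20 RD-X19 subjects with per-subject risk p over the full window, P(2 or more) = 1 - (1-p)^20 - 20p(1-p)^19. Take 76% of the risk as observed, which assumes risk is spread evenly over at-risk time.

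| Assumed p | Full window | 76% observed |
|---|---|---|
| 2% | 0.060 | 0.037 |
| 5% | 0.264 | 0.175 |
| 10% | 0.608 | 0.456 |
| 15% | 0.824 | 0.682 |

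With equal risk per treatment, Cohort 1's risk is p × 8/14. At p = 10% that is 5.7%, giving 0.318, still below the truncated 0.456 for Cohort 2.

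**The case against.** **The longer schedule would look safer than the shorter one.** A reader might infer this, and the documents do not support it. Both cohorts share the same reporting period and tabulation days. For the same visit day Cohort 2 never has less observed at-risk time than Cohort 1 (Step 4). Concurrent Cohort 2 sham subjects have the same cut-off, so that comparison loses events without being tilted by unequal follow-up.

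**The criterion is a pause trigger, not a comparison of schedules.** This is correct. The one planned interim analysis uses Cohort 1 only, where the window is complete at a Day 8 or 9 visit, so that review is essentially unaffected. But 8.5.1 also applies while Cohort 2 enrolls.

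**Serious events are covered elsewhere.** Largely true. Related SAEs remain reportable after the study. Laryngospasm, bronchospasm and anaphylaxis have their own 2-hour criterion. Volunteers are encouraged to report medically urgent AEs (4.1.1). The residual gap is non-serious reactions with onset after the final visit.

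**The 72 hours may be an attribution limit, not a promise of ascertainment.** The text does not say that it applies to each illumination, though that is a reasonable reading. As an attribution limit it leaves no literal contradiction, yet the count still omits reactions inside the limit that are never collected.

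**Practical impact is unshown.** This stands. The documents give no rate of delayed allergic reaction. In the 14-day Phase I study, 25 healthy volunteers reported only local site reaction, headache and nausea, typically resolving within 24 hours (5.2.1).

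**Longer collection adds background events.** Clarification Memorandum #1 records new COVID-19 symptoms from study day 4 as AEs, so extra days add some. Keeping the Day 1-8 tables contains this.

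**Conclusion.** The mismatch is real and does not depend on clock times: the window after Day 7 treatments ends on Day 10, and no visit or contact reaches that far. Under the assumed times, a Day 8 visit leaves 5 of 14 Cohort 2 treatments with an incomplete window and observes about 70-76% of continuous at-risk time. Cohort 1 loses nothing at a Day 8 visit and little at a Day 7 visit.

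The consequence is an under-count in Cohort 2 against its own criterion. Cohort 2 can look safer than it is. Its excess of continuous at-risk time over the 4-day schedule, 46-47% in full, appears as 2-11%. Truncation alone does not make it look safer than Cohort 1. The trigger probabilities are illustrations, since neither the risk nor its timing is known. If reactions cluster soon after illumination, the loss is smaller.

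Severity: minor to moderate.

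**What to change.** Reconcile protocol 8.5.1 with 9.2.1, the 4.2 schedule and SAP 5.6.1 on how the 72 hours are covered after the last treatment. As a data-collection change, collect AEs to at least 72 hours after the last treatment in both cohorts and both arms. Use one scheduled telephone AE contact where the final visit falls earlier, which will mainly concern Cohort 2. Keep the Day 1-8 tables, so that follow-up from first treatment stays comparable, and add a tabulation by time since last treatment. This takes no position on the length of the window or on the two-subject threshold.

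Cost: a short amendment; about one call per Cohort 2 subject (30, or up to 36 under Clarification Memorandum #2); closure 2-3 days later per subject; and a few extra background COVID-19 AEs. No added visit or sample is needed.
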